3.3.2 Exclusion Criteria

Subjects will be ineligible for this study if they meet **any** of the following criteria:

1. Hospitalization for evaluation or management of an infection within the last 8 weeks
2. Known organ dysfunction
 - Uncontrolled cardiovascular disease, including arrhythmias, congestive heart failure
 - Oxygen requirement
3. Addition of any new systemic immunosuppressive treatment within the last 2 weeks
 - Addition of new systemic immunosuppressive treatment along with glasdegib is also prohibited.

4. QTc interval >480 ms
5. Female patients who are lactating or have a positive serum pregnancy test
6. Major surgery within 14 days before enrollment
 - Does not include placement of venous access device, bone marrow biopsy, GVHD diagnostic biopsy, or other routine procedures in chronic GVHD or post-transplantation care
7. Use of any concomitant medications meds that are prohibited within the past 7 days
8. Any serious medical or psychiatric illness that could, in the investigator's opinion, potentially interfere with the completion of treatment according to this protocol
9. Known intolerance to glasdegib, sonidegib, or vismodegib
10. Non-hematologic malignancy within the past 2 years with the exception of:
 - adequately treated basal cell carcinoma, squamous cell skin cancer, or thyroid cancer
 - carcinoma in situ of the cervix or breast
 - prostate cancer of Gleason Grade 6 or less with stable prostate-specific antigen levels
 - cancer considered cured by surgical resection or unlikely to impact survival during the duration of the study
11. Treatment with non-FDA approved drug within 28 days of start of this trial
12. Evidence of recurrent or progressive underlying malignant disease
13. Karnofsky performance status < 70%
14. History of non-compliance
15. Life expectancy <6 months
16. Grade 2 or 3 muscle cramping, or grade 1 muscle cramping that occurs at least weekly

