1.3 THERAPY OF ESTABLISHED CHRONIC GVHD

Accepted standard primary therapy for cGVHD includes 0.5-1 mg/kg of prednisone or equivalent with or without a calcineurin inhibitor.^{1,18,19} The addition of other systemic immune-suppressive agents to initial therapy has not provided benefit, as evidenced by trials adding azathioprine, thalidomide, hydroxychloroquine, mycophenolate mofetil and entospletinib to initial treatment with steroids.²⁰⁻²³ Published primary cGVHD therapy trials demonstrate that on average 27% will achieve complete response, and 60% will achieve overall response (complete + partial response) by 6-9 months after starting initial therapy.^{18,20-24} A study testing the addition of ibrutinib to standard primary therapy has almost finished accrual as of December 2018.

Based on insufficient response to primary therapy or a flare of cGVHD after tapering of initial therapy, many will go on to require additional immune-suppressive agents for cGVHD control. “Steroid-refractory” cGVHD has most commonly been defined as either progressive manifestations despite one month of treatment, or incomplete response despite two months of 1-2 mg/kg of prednisone or equivalent.¹ In addition to steroid-refractoriness, other clinical indications for additional lines of systemic immune suppressive therapy include steroid dependence and steroid intolerance. Patients with steroid-dependent cGVHD can't tolerate tapering prednisone due to recurrent cGVHD manifestations. Steroid intolerant patients have medical complications of steroid therapy (e.g. hyperglycemia, edema, psychosis, osteoporosis), and thus require additional immune-suppressive agents to control GVHD and facilitate taper of prednisone. Multiple immune-suppressive therapies, including pharmacologic agents, monoclonal antibodies, and strategies such as extracorporeal photopheresis have demonstrated moderate activity in this setting, both ameliorating objective cGVHD manifestations, as well as facilitating taper of systemic steroids.²⁵ Their effectiveness is suboptimal, however, and many patients will require multiple agents to achieve disease control. A retrospective study showed that patients with cGVHD received a median of three lines of treatment and were on systemic immunosuppression for a median of 5 years. When patients stopped systemic treatment, between 30-50% of patients needed to restart treatment a median of 3-6 months later for recurrent symptoms.²⁶

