3.3 SELECTION OF STUDY POPULATION

3.3.1 Inclusion Criteria

Eligible subjects will be considered for inclusion in this study if they meet **all** of the following criteria:

1. At least 18 years old
2. Diagnosed with moderate or severe cGVHD according to the 2014 NIH Consensus Criteria
3. Diagnosed with cGVHD-related sclerosis or fasciitis
 - Skin feature score of at least 2 OR
 - Joints and fascia score of at least 1
4. New, stable or progressive sclerosis/faciitis despite treatment with at least one prior line of systemic therapy for cGVHD.
5. Female patients who:
 - Are documented to be postmenopausal or are surgically sterile, OR

- If of childbearing potential, agree to use at least 1 highly effective method of contraception from the time of signing the informed consent form through 30 days after the last dose of study drug, OR agree to practice true abstinence or exclusively non-heterosexual activity when this is in line with the preferred and usual lifestyle of the subject

6. Male patients who:

- Are surgically sterile (vasectomized) OR
- Agree to use at least 1 highly effective method of contraception during the entire study treatment period and through 30 days after the last dose of study drug, OR agree to practice true abstinence or exclusively non-heterosexual activity when this is in line with the preferred and usual lifestyle of the subject, AND
- Agree to use a condom to prevent potential transmission of investigational drug in seminal fluid

7. Patients who meet the following clinical laboratory criteria:

- Absolute neutrophil count (ANC) >1000/ μ L, platelet count >50 \times 10⁹/mL
- ALT and AST < 2x ULN and normal total bilirubin unless attributed to cGVHD
- Creatinine < 2.0 mg/dL

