3.3.3 Enrollment Procedures

Potentially eligible patients will be approached at participating study centers. The treating clinician will review the informed consent document with them. After the subject has signed and

dated the Informed Consent Form (ICF), screening may begin. Once all screening procedures have been completed and eligibility has been confirmed, the subject can be enrolled into the study. The screening period lasts from the date the subject signs consent until they complete the enrollment visit and start study drug, which may be up to 28 days.

Once 15 patients have been enrolled on study, the Coordinating center at Fred Hutchinson will assign screening slots to ensure that the study does not over-enroll.

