3.8 CONCOMITANT THERAPY

3.8.1 Permitted Concomitant Therapy

Standard supportive care medications are permitted as per institutional standards. These include infectious prophylaxis and symptomatic management, as well as ongoing (begun prior to study enrollment) systemic and topical therapies for acute or chronic GVHD. New topical therapies for cGVHD are also permitted and will not constitute treatment failure.

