5.5.2.2 Secondary Endpoints

The secondary endpoints are best overall Response Rate (ORR) in sclerotic manifestations, best ORR in all cGVHD manifestations, and safety.

Overall Response Rate (ORR) in sclerotic manifestations

Best ORR of sclerotic manifestations by 12 months after the initiation of glasdegib and before another systemic immunosuppressive regimen is started represents the composite outcome of complete and partial response (CR + PR). ORR will be calculated according to (1) the response definitions of the NIH Consensus Conference for (a) skin or joint scores (0-3), where improvement by at least 1 point is a PR and return to score 0 is a CR, or (b) the photographic range of motion scale (0-25) where improvement by at least 1 point is a PR and return to score 25 is a CR; and (2) change in the 0-10 sclerotic severity scale where at least a 2 point improvement is a PR or return to 0 (CR).

Overall Response Rate (ORR) in all cGVHD manifestations

Best ORR of all cGVHD manifestations by 12 months after the initiation of glasdegib and before another systemic immunosuppressive regimen is started represents the composite outcome of complete and partial response (CR + PR). ORR will be calculated according to the response

definitions of the NIH Consensus Conference. ORR both including and excluding skin sclerotic features will be reported.

Safety

Safety assessments will consist of monitoring and recording adverse events. See section 6.0 below.

In addition, we will describe the following exploratory endpoints:

Failure-Free Survival

This endpoint will be estimated at 12 months with events considered death, relapse, or start of another systemic immunosuppressive agent. Patients lost to follow-up or who withdraw consent will be censored.

Patient-reported outcomes

Subjects will provide assessments of their symptom burden and quality of life using a validated instrument recommended by the NIH Consensus on Chronic GVHD (Lee Chronic GVHD Symptom Scale) and the NIH-endorsed PROMIS-29 (See Appendix 10). These will be collected before starting glasdegib on day 1 of cycle 1, and again on D1, cycles 4, 7, 10, 13, 16, 19, 22 and EOT. Scores will be calculated for each instrument based on published algorithms with absolute changes from baseline and clinically meaningful changes described for the population as a whole and based on CR+PR vs. SD+MR+PD.

Biologic studies

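### A systemic agent added just over two weeks before entry may continue, and a later response to it can be counted in glasdegib's ORR; no planned analysis separates the two.

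*Combined protocol and SAP*

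**What the plan says.** Exclusion 3 in section 3.3.2 rules out "Addition of any new systemic immunosuppressive treatment within the last 2 weeks" and also prohibits adding such treatment together with glasdegib. It does not say whether the two weeks count back from consent, enrollment or first dose. Section 3.3.3 has the screening period run from consent to the start of study drug, "which may be up to 28 days".

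Inclusion 4 in section 3.3.1 asks for "New, stable or progressive sclerosis/faciitis despite treatment with at least one prior line of systemic therapy for cGVHD". It sets no minimum time on the most recent agent. Section 3.8.1 permits "ongoing (begun prior to study enrollment) systemic and topical therapies for acute or chronic GVHD".

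Section 5.3 analyses everyone who received any study drug. Section 5.5.2.2 takes best response up to 12 months after glasdegib starts and before another systemic immunosuppressive regimen is begun. The one split it plans for the all-manifestation ORR is by organ feature: "ORR both including and excluding skin sclerotic features will be reported". Section 5 contains no analysis by time since the last added agent.

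On timing, section 1.3 defines steroid-refractory disease as "progressive manifestations despite one month of treatment, or incomplete response despite two months of 1-2 mg/kg of prednisone or equivalent". The only response-timing figure there is that "60% will achieve overall response (complete + partial response) by 6-9 months after starting initial therapy". Section 1.4 reports a best ORR of 67% for ibrutinib as a later-line agent, without a time to response.

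**The concern.** The plan already accepts that another new agent confuses attribution. It prohibits adding one with glasdegib, and it ends the response window when one is started later. An agent started just over two weeks before entry gets no such treatment, although by the benchmarks in section 1.3 it has been given too briefly to be called a failure. Inclusion 4 does not close the gap: any earlier line satisfies it, and the sclerosis may be new or stable.

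There is no control arm. If such an agent works during the 12-month window, the response enters glasdegib's ORR and nothing in the analysis reveals it. At stake are the two secondary ORRs, the Simon rule in section 3.12 and the comparison with 67% in section 5.2.

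**Working it through.** **Timing.** The earliest eligible addition is 15 days before the reference date. If the two weeks count back from consent, first dose falls about 15 days (no screening gap) to 15 + 28 = 43 days after the addition. In either case, months 6 to 9 after the addition lie inside the 12-month response window.

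**Reproducing the plan's design.** Section 3.12 gives a null ORR of 20%, an alternative of 50%, suspension if 2 or fewer of the first 10 respond, and rejection of the null if 8 or more of 19 respond. The probability of meeting the rule at true rate p is

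R(p) = sum over x = 3 to 10 of P(X1 = x) × P(X2 ≥ 8 − x), with X1 ~ Bin(10, p) and X2 ~ Bin(9, p).

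- R(0.20) = 0.0223. The stated 0.025 is the nominal ceiling.
- R(0.50) = 0.808, in line with the stated 80%.
- The chance of stopping at stage 1 when p = 0.20 is 0.678.

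**Effect of recent add-on patients.** Let f be the share of patients who entered soon after adding an agent, and q their total response rate. Everyone else responds at the null rate. The mixed rate is p = 0.20(1 − f) + q·f, and it goes into the same exact formula.

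The documents do not give f; 5%, 10% and 20% (1, 2 and 4 of 20 patients) are assumptions. For q, 60% is the initial-therapy figure in section 1.3, 67% is the ibrutinib figure in section 1.4, and 30% is an assumed low value.

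| q | f = 5% | f = 10% | f = 20% |
|---|---|---|---|
| 30% | p = 0.205, R = 0.026 | p = 0.210, R = 0.029 | p = 0.220, R = 0.038 |
| 60% | p = 0.220, R = 0.038 | p = 0.240, R = 0.060 | p = 0.280, R = 0.129 |
| 67% | p = 0.2235, R = 0.041 | p = 0.247, R = 0.070 | p = 0.294, R = 0.161 |

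For example, with q = 67% and f = 20%: p = 0.20 × 0.80 + 0.67 × 0.20 = 0.294.

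The expected excess of responses in 20 patients is 20 × (p − 0.20). It runs from 20 × 0.005 = 0.1 to 20 × 0.094 = 1.9.

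**Futility side.** At f = 20% the chance of stopping at stage 1 falls from 0.68 to 0.44 (q = 60%) or 0.40 (q = 67%), although the other patients still respond at the null rate.

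**The case against.** Several stronger readings are tempting, and the documents do not support them.

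- A reader might infer that the plan itself dates an added agent's response to between one and nine months. It does not. One and two months mark failure of prednisone, not onset of response. The 6-9 month figure is cumulative and belongs to initial therapy. Ibrutinib has no time to response at all.
- A reader might say that such responses are counted. The documents support only that they can be, because the number of affected patients is unknown and may be zero.
- A reader might think that the 21-day look-back for concomitant medication in section 4.1.4 would miss these agents. It would not: an agent still being taken falls within that window whatever its start date. Section 5.4 refers to concomitant-medication start dates, so some are evidently collected. What remains is that section 5.4 allows missing or partial dates to be imputed, which is unsuitable for a classification that turns on weeks.
- A reader might infer that the 20% null excludes any contribution from background therapy. Section 3.12 gives no derivation of 20%, so this cannot be said.
- A reader might add the two agents' effects as if independent, using p = 0.20 + 0.80·f·q. With f = 20% and q = 67% this gives 0.19 instead of 0.16. The documents give no basis for independence, so the lower model is used here.

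Two further objections limit the size. The 60% comes from initial therapy, whereas these patients have had at least one prior line. Section 1.3 also calls sclerotic forms much harder to treat, so 60-67% may overstate the bias in the sclerotic ORR. Finally, the primary endpoint is safety and tolerability, and the Simon design is introduced as a futility rule. Both are correct, but section 3.12 also states when the null is rejected, and section 5.2 plans a comparison with 67%, so an efficacy reading is foreseen.

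**Conclusion.** The gap is in the text. Eligibility, permitted therapy and the response definition together allow a response to a recently added agent to be credited to glasdegib, and no planned analysis would show it.

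The size depends on a share that the documents do not give. With 5-20% of patients affected, responding at 30-67%, and the rest at 20%, the chance of meeting the 8-of-19 rule is about 0.03-0.16 instead of 0.022. Even the mildest case (0.026) is just above the nominal 0.025. The calculation treats all patients as sharing one mixed rate, and its upper end is less credible for the sclerotic ORR than for the all-manifestation ORR. The primary safety endpoint is unaffected. This is a correctable weakness in the secondary efficacy analyses, not a flaw in the trial's main purpose.

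**What to change.** 1. Prespecify that both ORRs are reported in all treated patients and again, as a descriptive sensitivity analysis with exact confidence intervals, excluding patients who added a systemic cGVHD or immunosuppressive agent within 8 weeks before C1D1. Eight weeks matches the two-month failure point in section 1.3. The 8-of-19 rule should not be applied to this smaller set.
2. Because 8 weeks does not cover the 6-9 month response period, list each responder's time since the last added agent. Qualify any efficacy conclusion that rests on recent add-on patients.
3. Require complete, non-imputed start dates for every ongoing systemic agent.
4. State the date from which the two weeks in exclusion 3 are counted.

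The cost is one additional analysis, a listing and tighter date capture. The sensitivity set is smaller and its intervals wider. The analysis and listing can be added even if accrual is complete. Whether the interval in exclusion 3 should be reconciled with section 1.3 is for the sponsor to decide; the analysis does not depend on it.

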3.3.3 Enrollment Procedures

Potentially eligible patients will be approached at participating study centers. The treating clinician will review the informed consent document with them. After the subject has signed and

dated the Informed Consent Form (ICF), screening may begin. Once all screening procedures have been completed and eligibility has been confirmed, the subject can be enrolled into the study. The screening period lasts from the date the subject signs consent until they complete the enrollment visit and start study drug, which may be up to 28 days.

Once 15 patients have been enrolled on study, the Coordinating center at Fred Hutchinson will assign screening slots to ensure that the study does not over-enroll.

3.4 STUDY DRUG

3.4.1 Premedications

No specific premedications or supporting medications are required in conjunction with glasdegib administration.

3.4.2 Formulation, Packaging, and Storage

Glasdegib tablets will be provided by Pfizer Worldwide Research and Development from clinical supply. The study drug will be labeled and handled as open-label material, and packaging labels will fulfill all requirements specified by governing regulations. Glasdegib will be supplied as 25 mg tablets for oral administration.

Glasdegib will be packaged in high-density polyethylene bottles and should be handled with care. Each bottle will contain enough medication for the appropriate number of doses between study visits (one cycle worth dispensed at cycles 1-6, and three cycles' worth dispensed at cycles 7 and beyond), plus an additional amount to cover the allowed time windows around visit scheduling. Patients should be instructed to keep their medication in the bottles provided and not transfer it to any other containers and return the bottles to the site at the next study visit. Site personnel must ensure that patients clearly understand the directions for self-medication.

Investigational product should be dispensed by an appropriately qualified and experienced member of the study staff (e.g., physician, nurse, physician's assistant, practitioner, or pharmacist) as allowed by local, state, and institutional guidance.

Investigational glasdegib that will not be used (expired, returned, or leftover at end of study) should be destroyed on site according to the institution's standard operating procedure, and removal and destruction must be documented on drug accountability logs.

3.4.3 Administration of Study Drug

Glasdegib will be administered at a dose of 50 mg once daily by mouth. Up to 24 months of glasdegib treatment will be administered on study. Glasdegib is 77% bioavailable with a time to peak concentration of less than 2 hours. The drug is metabolized through the CYP3A4 pathway with a half life of 17 hours. Steady state is reached after 8 days.

At any time, patients may hold glasdegib because of side effects, toxicity or for logistic reasons. Any number of doses may be held as long as drug is resumed within 28 days. If glasdegib is held for longer than 28 days, it should not be restarted and the patient is just followed for clinical endpoints.

All protocol-specific criteria for administration of study drug must be met and documented before drug is started. Study drug will be administered or dispensed under the supervision of the investigator or identified sub-investigators. Subjects should be monitored for toxicity, and doses of glasdegib should be modified as needed to accommodate subject tolerance to treatment.

Glasdegib will be self-administered by the patient at home, unless otherwise specified. Glasdegib will be administered orally with approximately 8 ounces (240 mL) of water and should be taken in the morning, at the same time each day with or without food. Tablets must not be crushed or cut; they must be swallowed whole, not manipulated or chewed prior to swallowing. Patients should be instructed to not to take more than the prescribed dose at any time. If a patient forgets to take their dose at the regularly scheduled time, and if less than 10 hours have passed since the scheduled dosing time, that dose should be taken as soon as possible. If more than 10 hours have passed since the scheduled dosing time, the dose should be skipped and the patient should continue on their normal dosing schedule. If a patient misses a day's dose entirely, they must be instructed not to "make it up" the next day. If a patient vomits any time after taking a dose, they must be instructed not to "make it up," but to resume subsequent doses the next day as prescribed. If a patient inadvertently takes 1 extra dose during a day, the patient should not take the next dose of glasdegib.

3.4.4 Assuring Subject Compliance

Study patients will document their compliance through medication logs. The subject study drug diary is provided in Appendix 3.

3.5 STUDY TREATMENT SCHEDULE

Glasdegib will be administered at a dose of 50 mg once daily by mouth. Up to 24 months of glasdegib treatment will be administered on study.

3.6 DURATION OF THERAPY

Subjects will be treated with glasdegib for up to 24 months depending on tolerability and response.

3.7 DOSING DELAYS AND MODIFICATIONS

Subjects should be followed closely for AEs or laboratory abnormalities that might indicate glasdegib-related toxicity. If a subject experiences a treatment-related toxicity of grade 3 or higher or other intolerable treatment-related AE of any grade during the course of therapy, then glasdegib should be withheld or the dose reduced, as necessary, until the AE resolves to grade ≤ 2 or stabilizes to an acceptable degree.

As appropriate, certain laboratory abnormalities may warrant more frequent monitoring (e.g., once per week) until abnormalities have recovered to Grade ≤ 1 .

Treatment with glasdegib should be withheld for any unmanageable, potentially study-drug-related toxicity that is Grade ≥ 3 in severity or for QTc greater than 500 ms. Any other clinically important events where dose delays may be considered appropriate must be discussed with the Principal Investigator. If glasdegib needs to be held for more than 28 days for a treatment-related toxicity, it should not be restarted.

